## SYNOPSIS

### TITLE OF TRIAL

An open-label trial investigating the pharmacokinetics of FE 999049 given as a single subcutaneous dose in gonadotropin down-regulated healthy Chinese women

### TRIAL SITE

One trial site in China.

### PLANNED TRIAL PERIOD

The first subject is expected to be enrolled in 2019 with a total duration of the trial of approximately 7 months.

### CLINICAL PHASE

1

### BACKGROUND AND SCIENTIFIC JUSTIFICATION FOR CONDUCTING THE TRIAL

FE 999049 is a gonadotropin preparation containing recombinant human follicle stimulating hormone (rhFSH) under development by Ferring Pharmaceuticals for controlled ovarian stimulation for the development of multiple follicles in women undergoing assisted reproductive technologies (ART) such as in vitro fertilisation (IVF) or intracytoplasmic sperm injection (ICSI) cycle. In previous trials the exposure to and dose proportionality of FE 999049 in a clinically relevant dose range in Caucasian and Japanese healthy women have been shown to be very similar. This is a trial in healthy Chinese women investigating the pharmacokinetics, safety, and tolerability of a single subcutaneous dose of FE 999049.

### OBJECTIVES

The objectives of the trial are to:

- Investigate the single-dose pharmacokinetics of FE 999049 administered as a subcutaneous abdominal injection in healthy Chinese women
- Investigate the safety and tolerability of a single dose of FE 999049 administered as a subcutaneous abdominal injection in healthy Chinese women

### METHODOLOGY

This is an open-label, randomised parallel group trial investigating the pharmacokinetics of FE 999049 after a single subcutaneous abdominal injection of 12, 18, or 24 µg, with 8 healthy Chinese women in each dose group.

Blood samples for analysis of FE 999049 concentration will be collected during 10 days.

Premenopausal women are chosen as trial population to mimic the target patient population. In order to minimise the interference by endogenous FSH with the pharmacokinetic assessment of the recombinant FSH, a gonadotropin releasing hormone (GnRH) receptor agonist, DECAPEPTYL Depot, will be administered throughout the trial period to suppress the endogenous release of FSH.

The doses in the trial are chosen to cover a possible range of clinical dosing of FSH in the targeted indications, however restricted at the lower end due to analytical constraints.

## NUMBER OF SUBJECTS

24 healthy Chinese women will be included and dosed.

## CRITERIA FOR INCLUSION / EXCLUSION

Healthy Chinese women, 21-40 years of age with a normal menstrual cycle (24-35 days), may be included in this trial. The complete list of inclusion and exclusion criteria is provided below.

### Inclusion Criteria

1. Signed written Informed Consent Form
2. Female of Chinese origin, with two ethnic Chinese parents and four ethnic Chinese grandparents
3. 21–40 years of age (both inclusive)
4. Willing to stop using combined oral contraceptives (COC) in relation to the first DECAPEPTYL Depot administration on Day -28
5. Agrees to use a double barrier method of contraception between Day -63 and Day 28, if not abstinent. A double barrier method of contraception should also be used after Day 28 until menses resumes or until another contraceptive method has been established
6. Normal menstrual cycles with a range of 24-35 days in the absence of oral contraceptives
7. Serum follicle-stimulating hormone (FSH)  $\leq$  5 IU/L on Day -3 and Day -1
8. Body mass index (BMI) of 18.5 -25 kg/m^2 (both inclusive)
9. Negative serology for human immunodeficiency virus (HIV) antibody, hepatitis B (surface antigen), hepatitis C antibody, and syphilis bacteria
10. Healthy according to medical history, physical examination, gynaecological examination, electrocardiogram (ECG), blood pressure, and laboratory profile of blood and urine
11. Negative urine drug screen and alcohol breath test at screening and on Day -1
12. Non-smoker or light smoker ( $\leq$  5 cigarettes/day) for at least 6 months prior to trial start

## Exclusion Criteria

1. Presence or a history of clinically significant diseases of the renal, hepatic, gastrointestinal, cardiovascular, or musculoskeletal systems, or presence or history of clinically significant reproductive, psychiatric, immunological, endocrine or metabolic diseases
2. Cancer within the last 5 years except for adequately managed basal cell carcinoma and squamous cell carcinoma of the skin
3. Pregnancy or breastfeeding
4. Current or a history of endocrine abnormalities such as hyperprolactinaemia, polycystic ovary syndrome or other ovarian dysfunction, tumours of the pituitary gland or hypothalamus, thyroid or adrenal disease
5. Clinically significant findings on the trans-vaginal ultrasound, cytology, gynaecological or breast examination at screening or on Day –1 including ovarian cysts or tumours of the ovaries or uterus
6. Contraindications for the use of gonadotropins and gonadotropin-releasing hormone (GnRH) agonists
7. Previously treated with gonadotropins within the last 6 months prior to screening
8. History within the last two years or current abuse of alcohol or drugs
9. Presence or history of severe allergy or anaphylactic reactions
10. Intake of prescribed medication, over-the-counter (OTC) medication, or herbal medicines, with the exceptions of COC, cromoglycate, and paracetamol according to the labelling, within 2 weeks or 5 half-lives of the drug, whichever is longer, prior to first dose of DECAPEPTYL Depot. Topical treatments of bacterial or fungal infection are allowed if stopped before first dose of IMP.
11. Intake of any non-registered investigational drug within the last 12 weeks preceding screening, or longer if judged by the investigator to possibly influence the outcome of the current trial
12. High daily consumption of caffeine-containing beverages (e.g. more than five cups of coffee or equivalent) with a risk of withdrawal symptoms arising during the trial that may confound the safety evaluation
13. Blood donation or major blood loss ( $\geq 500$  mL) within the last 8 weeks, or plasma donation with the last 4 weeks preceding the first day of IMP dosing
14. Current non-smokers or light smoker with a history of long-term, heavy smoking ( $>10$  pack-years)
15. Previously dosed in this trial
16. Mental incapacity or language barrier precluding adequate understanding or co-operation

17. Considered by the investigator to be unsuitable to participate in the trial for any other reason

## **MEDICINAL PRODUCTS**

### Investigational medicinal product

- FE 999049 is provided as a cartridge with 72 µg rhFSH in 2.16 mL and an injection pen

### Non-investigational product

- DECAPEPTYL Depot 3.75 mg

## **DURATION OF TREATMENT**

Each subject is planned to receive a single injection of FE 999049. For each subject, the duration of the trial including screening and follow-up visits will not exceed 13 weeks.

## **ENDPOINTS**

- Pharmacokinetics (AUC, AUCt, Cmax, tmax, CL/F, Vz/F, t1/2)
- Safety (ECG, vital signs, laboratory parameters, adverse events)
- Injection site reactions
- Presence of anti-FSH antibodies

## **TRIAL PROCEDURES / ASSESSMENTS**

Before inclusion into the trial, all subjects will undergo a general physical and a gynaecological examination, including vital signs, ECG, transvaginal ultrasonography and cytology as well as laboratory assessments including haematology, clinical chemistry, and urinalysis.

The subjects will receive two administrations of a 1-month depot formulation of DECAPEPTYL Depot 3.75 mg to down-regulate endogenous release of FSH during the trial. The first DECAPEPTYL Depot administration will be given 28±1 days prior to the first dose of IMP. In women not receiving hormonal contraceptives, the first DECAPEPTYL Depot administration should take place in the time interval 7 days before to 3 days after the expected start of menstruation. In women discontinuing combined oral contraceptives, the first DECAPEPTYL Depot administration should take place after the subjects have discontinued the hormonal contraception and within 5 days of commencement of bleeding. A second administration will be given 10±1 days prior to the first IMP administration.

To verify low stable endogenous hormones, serum FSH will be measured at Day -3 and Day -1. If any of the measurements is >5 mIU/mL, the subject will be excluded.

Subjects will come for a residential stay, lasting between Day -1 and Day 3, and ambulatory visits or, if agreed between investigator and subject, a residential stay from Day 4 to Day 10. A follow-up visit will be performed on Day 11. Blood samples for pharmacokinetic (PK) analysis of FE 999049 will be collected from Day 1 to Day 10, every 4 hours during the first 48 hours and then once daily.

Safety and tolerability will be assessed in terms of AEs, vital signs, ECG, and safety laboratory parameters up to and including Day 11. On Day 1, Day 7 and Day 28, assessment of the presence of anti-FSH antibodies will be performed.

## **STATISTICAL METHODS**

### Pharmacokinetic analysis

Pharmacokinetic parameters will be calculated using non-compartmental methods and evaluated using descriptive statistics. Dose proportionality will be investigated for AUC and  $C_{max}$ .

### Safety

Safety endpoints will be evaluated by data listings and descriptive statistics.

## LIST OF ABBREVIATIONS

ADR	adverse drug reaction
AE	adverse event
AMH	anti-Müllerian hormone
ANOVA	analysis of variance
ART	assisted reproductive technology(ies)
ATC	anatomical therapeutic chemical classification system
βhCG	beta unit of human chorionic gonadotropin
BMI	body mass index
CFDA	China Food and Drug Administration
CHO	Chinese hamster ovary
COC	combined oral contraceptive
COS	controlled ovarian stimulation
CRO	clinical research organisation
CV	coefficient of variation
ECG	electrocardiogram
e-CRF	electronic case report form
FAS	full analysis set
FDA	Food and Drug Administration, USA
FSH	follicle-stimulating hormone
GCP	Good Clinical Practice
GMP	Good Manufacturing Practice
GnRH	gonadotropin-releasing hormone
HIV	human immunodeficiency virus
ICH	International Conference on Harmonisation
ICSI	intracytoplasmic sperm injection
IEC	independent ethics committee
IMP	investigational medicinal product
IRB	institutional review board
IVF	in vitro fertilisation
LLQ	lower limit of quantification
MCH	mean corpuscular haemoglobin content
MCHC	mean corpuscular haemoglobin concentration
MCV	mean cellular volume
MedDRA	Medical Dictionary for Regulatory Activities
NCA	non-compartmental analysis
NIMP	non-investigational medicinal product
OHSS	ovarian hyperstimulation syndrome
OTC	over-the-counter
PD	pharmacodynamic(s)
PK	pharmacokinetic(s)
PP	per protocol

---

rhFSH	recombinant human follicle stimulating hormone
SAE	serious adverse event
SAP	statistical analysis plan
SOC	system organ class
WHO	World Health Organization

## DEFINITION OF TERMS

### Definition of general terms

Enrolled	When subject and investigator have signed the Informed Consent Form
Included	When the subject has been dosed with investigational medicinal product (IMP)
Pre-dose	Before dosing on the day of IMP dosing
Treatment period	Time from administration of the IMP until discharge from the clinic at Visit 12
End-of-trial	The last visit (Visit 14) for the last subject

### Pharmacokinetic terms and definitions

AUC	Area under the concentration-time curve from dosing to infinity
AUC t	Area under the concentration-time curve from dosing up to time t, where t is the last time point at which the concentration is above the lower limit of quantification.
% Extrap AUC	Percentage of AUC that is due to extrapolation from the last measurable concentration
CL/F	Apparent total systemic clearance
C max	Maximum concentration observed
λ z	First-order rate constant associated with the terminal (log-linear) portion of the concentration-time curve
NCA	Non-compartmental analysis
t 1/2	Terminal elimination half-life
t max	Time of maximum observed concentration (C max )
V z/F	Apparent volume of distribution associated with the terminal phase

## 1 INTRODUCTION

### 1.1 Background

FE 999049 is a gonadotropin preparation containing recombinant human follicle-stimulating hormone (rhFSH) under development by Ferring Pharmaceuticals. It is intended for controlled ovarian stimulation for the development of multiple follicles in women undergoing assisted reproductive technologies (ART) such as an in vitro fertilisation (IVF) or intracytoplasmic sperm injection (ICSI) cycle.

FE 999049 is developed from a human cell line, in contrast to the commercially available rFSH products that are derived from Chinese hamster ovary (CHO) cell lines. In December 2016, Ferring received Marketing Authorisation approval from the European Commission for FE 999049 under the trade name REKOVELLE. During 2017, FE 999049 was approved in Australia, Brazil, Israel, and Switzerland, and in 2018, also in Mexico and Canada.

Before the current trial, Ferring has completed four phase 1 trials (CS01, CS02, CS03 and 000020, all conducted in US), two phase 2 dose-response trials (000009 conducted in EU and 000124 conducted in Japan) and two phase 3 trials (000004 and 000071 conducted in Europe and Rest of World) as part of the clinical development programme for FE 999049. A total of 1,927 subjects have been included in the completed clinical trials, of whom 1,112 subjects were exposed to FE 999049. Momentarily, two phase 3 trials are ongoing (a Pan-Asian trial conducted in China, Taiwan, South Korea, and Vietnam and one conducted in Japan) including approximately 1,328 subjects in total of whom approximately 664 subjects will be randomised to treatment with FE 999049.

Of the four previous phase 1 trials, CS01, CS03, and 000020 were single dose trials conducted in healthy female subjects. These trials showed that FE 999049 is absorbed slowly after single subcutaneous administration, with the median  $t_{max}$  ranging from 10 to 24 hours. Mean absolute bioavailability of FE 999049 given subcutaneously was determined to be 64%. Single subcutaneous administration of increasing doses to healthy female subjects indicated dose proportionality of  $C_{max}$  and AUC over a wide dose range of 8.8 to 26.3  $\mu$ g (based on conversion from IU to  $\mu$ g for the specific batch used). Thus, the data demonstrated that the exposure to FE 999049 increased proportionally with doses across the whole therapeutic dose range up to 24  $\mu$ g FE 999049 (24  $\mu$ g being the maximum dose in the phase 3 programme and in the proposed posology for repeated cycles). The fraction of FE 999049 excreted unchanged in urine was approximately 11%. Comparisons between Japanese and Caucasian women following administration of 450 IU FE 999049 demonstrated similar exposure by means of AUC and  $C_{max}$ . Also the PK parameters  $t_{max}$ ,  $t_{1/2}$ , CL/F, and  $V_z/F$  were similar for the Japanese and Caucasian women. Single dose administration of FE 999049 was safe and well tolerated as assessed by AEs, vital signs, ECG, clinical laboratory measurements, and physical examination. There were no signs of any anti-FSH antibody formation or allergic reactions. No serious adverse event or death occurred during the trials.

One previous phase 1 trial, CS02, evaluated daily subcutaneous administration of 225 IU FE 999049 in healthy female subjects. This trial showed that a steady-state level of FSH was reached on treatment day 6-7 at which time the  $C_{max}$  concentrations were 2.5- to 3-fold higher than those obtained after a single dose. The terminal half-life of FE 999049 was 28 hours after multiple subcutaneous administrations, which was shorter than the average of 40 hours after single subcutaneous administration. The time to maximal concentration was also shorter after multiple compared to single subcutaneous administration, with medians of 10 hours versus 24 hours, respectively. The reason for this is as yet unknown, but these differences have also been observed for other FSH preparations.

The two phase 2 trials 000009 and 000124 were randomised, controlled, assessor-blind, multi-centre dose-response trials in which randomisation was stratified according to the subject's anti-Müllerian hormone (AMH) level at screening. In both trials, a statistically significant dose-response relationship for FE 999049 with respect to the number of oocytes retrieved was observed. Furthermore, the dose-response relationship observed in Japanese and European subjects was similar. The similarity of the dose-response relationship between Japanese and European subjects supported the pharmacological rationale of the individualised treatment regimen.

During the two phase 3 trials 000004 and 000071, 665 IVF/ICSI subjects were treated with FE 999049 in 1,012 treatment cycles. The two trials supported the efficacy and safety of FE 999049 in the proposed indication with the individualised FE 999049 dosing regimen based on AMH level (measured by Elecsys® AMH Immunoassay, Roche Diagnostics) and body weight.

The ongoing phase 3 trial in Pan Asia is a randomised, controlled, assessor-blind, parallel groups, multicentre, non-inferiority trial comparing the efficacy and safety of FE 999049 and GONAL-F.

The ongoing phase 3 trial in Japan is a randomised, controlled, assessor-blind, parallel groups, multicentre, non-inferiority trial assessing the efficacy and safety of FE 999049 versus FOLLISTIM.

## 1.2 Scientific Justification for Conducting the Trial

This is a trial with the overall objective to obtain data on the pharmacokinetics of FE 999049 in healthy Chinese women. The trial will support the registration of FE 999049 in China.

## 1.3 Benefit / Risk Aspects

This is a phase 1 trial in healthy subjects and does not entail any medical benefit for the trial participants.

FE 999049 is a recombinant human FSH, and it is expected that the pharmacological effects and side effects of FE 999049 resemble those reported for other FSH products. The most frequently reported AEs in a previous single dose trial with FE 999049 in Caucasian women at doses ranging from 37.5 IU to 450 IU were headache and injection site reactions, the latter of short duration and possibly related to the volume administered. In another previous single dose trial with FE 999049 in Japanese and Caucasian women at doses ranging from 75 IU to 450 IU, the most frequently reported AEs were lower abdominal pain, vaginal haemorrhage and injection site reactions. In both trials a limited number of other AEs were sporadically reported in all treatment groups, including the placebo groups, and FE 999049 was regarded well tolerated. In the third previous single dose trial with FE 999049 in Caucasian women receiving 450 IU, the most frequently reported AEs were headache, breast tenderness and pelvic discomfort. Common side effects reported for other FSH products are ovarian enlargement, breast complaints, abdominal pain, pelvic pain, headache, gastrointestinal symptoms, injection site reactions (swelling, pain, redness), hypersensitivity reactions, and ovarian cysts. Cases of ovarian hyperstimulation syndrome (OHSS), characterised by large ovarian cysts, abdominal pain, abdominal distension, vascular leakage, and rarely associated with thromboembolic events, have occurred in multiple dose trials with other FSH products, but no signs of OHSS were observed in the previous phase 1 trials.

Adverse drug reactions following treatment with GnRH agonists such as DECAPEPTYL Depot include, but are not restricted to, hot flushes, decreased libido, mood changes, headache, abdominal pain and menstrual disorders that may be related to the induced transient oestrogen deficiency. Functional follicular cysts may occur upon treatment with GnRH agonists, the incidence being up to 9.3 %. In this trial, the subjects will undergo an ultrasound examination prior to the administration of the investigational medicinal product (IMP), and those who have developed cysts will be withdrawn from the trial. Without gonadotropin stimulation, these cysts have virtually no clinical significance in a healthy woman.

Overall, the risks posed to the subjects participating in the trial are deemed low and ethically justifiable. For more detailed information on FE 999049 please refer to the Investigator's Brochure.

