### 2.2 Endpoints

- Pharmacokinetics (AUC, AUCt, Cmax, tmax, CL/F, Vz/F, t1/2)
- Safety (ECG, vital signs, laboratory parameters, adverse events)
- Injection site reactions
- Presence of anti-FSH antibodies

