#### Non-investigational Medicinal Product

The subjects will receive two subcutaneous abdominal injections of a 1-month depot formulation of the GnRH agonist DECAPEPTYL Depot 3.75 mg (Triptorelin).

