## 6 TRIAL PROCEDURES

The trial comprises 14 visits, 1 of which is the residential treatment visit. The duration of the trial including the screening period and the follow-up visits will not exceed 13 weeks.

Assessments of AEs and concomitant medication will be performed throughout the trial.

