**Table 1 Trial flow chart**

Visit No. Day	Screening	Run-in period				Treatment and Assessments								Follow-up	Anti-FSH ab		
		Ambulatory visits				Residential stay				Ambulatory visits							
	1	2	3	4	5	6	7	8	9	10	11	12	13	14			
-63 to -29	-28	-10	-3	-1	1	2	3	4	5	6	7	8	9	10	11	28	
Inclusion/exclusion criteria	X				X												
Informed Consent	X																
Randomisation					X												
Demographics	X																
Physical examination	X															X	
Medical history	X																
Gynaecological exam. and transvaginal ultrasound	X			X a	X a											X	
Cytology	X b															X	
Serum pregnancy test	X				X											X	
Urine pregnancy test		X c	X c														
FSH for eligibility determination (local laboratory)				X	X												
Blood sampling for PK determination						X d	X d	X d	X	X	X	X	X	X			
Urine drugs screen	X				X												
Alcohol breath test	X				X												
Serology	X																
Vital signs e	X			X	X f	X f	X f									X	
12-lead ECG	X			X	X f	X f	X f									X	
Clinical chemistry, haematology, and urinalysis	X			X				X								X	
Injection site reactions					X g												
Blood sampling for anti-FSH antibody analysis					X h						X					X	
Adverse events	X	X	X	X	X	X	X	X	X	X	X	X	X	X	X	X	
Prior/concomitant medication	X	X	X	X	X	X	X	X	X	X	X	X	X	X	X	X	
Administration of DECAPEPTYL Depot 3.75 mg		X	X														
Administration of IMP					X												

ab: antibody; ECG: electrocardiogram; FSH: follicle-stimulating hormone; IMP: investigational medicinal product; PK: pharmacokinetic;

a) Between Day -3 and Day -1

b) Cytology will be performed at screening if not done within 6 months prior to screening

c) Before the Day -28±1 and Day -10±1 DECAPEPTYL Depot administration

d) -1, -0.5, 0, 4, 8, 12, 16, 20, 24, 28, 32, 36, 40, 48 hours post-dose

e) Vital signs include systemic blood pressures, heart rate and body temperature

f) 12, 24 and 48 hours post-dose

g) Immediately, and 30 min and 24 hours after administration

h) Before administration of FE 999049

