#### 7.1.3 Other Assessments related to Endpoints

##### 7.1.3.1 Injection Site Reactions

Injection site reactions will be assessed by the investigator immediately after injection, 30 minutes, and 24 hours after administration of the IMP. The injection site reactions to be assessed are redness, pain, itching, swelling, and bruising, each to be assessed as none, mild, moderate, or severe. These injection site reactions will not be recorded as AEs.

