10.5 Injection Site Reactions

Injection site reactions will be summarised by treatment with the number and percentage of subjects experiencing none, mild, moderate, or severe grade of redness, pain, itching, swelling, and bruising, or any of these symptoms, immediately after injection, 30 minutes after injection, 24 hours after injection, or at any of these time points.

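### Injection site reactions are graded at 0 h, 30 min and 24 h with no worst-since-last grade, so a listed reaction that comes and goes between 30 min and 24 h can be missing from both the endpoint table and the adverse event tables

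*Protocol*

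**What the plan says.** Protocol Section 2.2 and SAP Section 2.2 list "Injection site reactions" as an endpoint in its own right, beside the general safety endpoint.

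Protocol Section 7.1.3.1 sets the schedule: "Injection site reactions will be assessed by the investigator immediately after injection, 30 minutes, and 24 hours after administration of the IMP". Footnote g of Table 1 agrees: "Immediately, and 30 min and 24 hours after administration". Redness, pain, itching, swelling and bruising are each graded from none to severe. The same section then closes the adverse event route: "These injection site reactions will not be recorded as AEs".

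Protocol Section 9.7.3.5 and SAP Section 10.5 tabulate the grades "immediately after injection, 30 minutes after injection, 24 hours after injection, or at any of these time points". Neither document asks for the worst grade since the preceding score.

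As background, Protocol Section 1.3 describes the leading events in one earlier single-dose trial as "headache and injection site reactions, the latter of short duration and possibly related to the volume administered". For a second trial it names injection site reactions among the most frequent events without giving a duration. On adverse events in general, Protocol Section 6 says: "Assessments of AEs and concomitant medication will be performed throughout the trial".

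**The concern.** With three separate gradings and no recall item, what is tabulated is what is found at those three moments. A listed reaction that starts after the 30-minute score and resolves before the 24-hour score is graded none each time. It then adds nothing to the any-time row, which a reader will take as the cumulative incidence over the day.

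The adverse event tables are not a clear backstop, since Section 7.1.3.1 keeps these reactions out of adverse event recording. The protocol does not say whether that exclusion also covers a listed reaction noticed between scores.

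What is at stake is the completeness of one descriptive tolerability endpoint. With 8 women per dose group, each woman missed moves a group rate by 1/8 = 12.5 percentage points.

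**Working it through.** **Inputs from the documents.** Scores at 0, 0.5 and 24 h (Protocol 7.1.3.1; Table 1 footnote g). Summaries use those three times or any of them (Protocol 9.7.3.5; SAP 10.5). Eight women per group (Protocol 3.1.2). The plan states no detection rate or expected incidence for this endpoint, so there is no figure of its own to reproduce.

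**Step 1: the gaps.** 0.5 − 0 = 0.5 h and 24 − 0.5 = 23.5 h.

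**Step 2: when a reaction is missed.** A reaction with onset u and duration D (hours) escapes every score when u > 0.5 and u + D < 24. Short duration alone is not enough: the onset must also fall after 30 minutes.

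**Step 3: how the loss depends on onset (assumed inputs).** Take onset uniform on (0, W] and a fixed duration D of at least 0.5 h. Then

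missed share = max(0, min(W, 24 − D) − 0.5) / W.

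| Onset window W | Duration D | Missed share |
|---|---|---|
| 0.5 h | 0.5 to 23 h | 0% |
| 2 h | 0.5 to 12 h | (2 − 0.5)/2 = 75% |
| 2 h | 23 h | (1 − 0.5)/2 = 25% |
| 24 h | 1 h | (23 − 0.5)/24 = 94% |
| 24 h | 4 h | (20 − 0.5)/24 = 81% |
| 24 h | 12 h | (12 − 0.5)/24 = 48% |
| 24 h | 23 h | (1 − 0.5)/24 = 2% |

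The result runs from 0% to 94% on the assumption alone.

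**Step 4: reactions assumed to start after 30 minutes.** Take onset uniform on 0.5 to 12 h and exponential duration with mean m. Only the 24 h score can see such a reaction, so

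d = (m / 11.5) × [exp(−12/m) − exp(−23.5/m)].

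- m = 2 h: d = 0%
- m = 4 h: d = 2%
- m = 8 h: d = 12%
- m = 12 h: d = 24%

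These are detection rates among late-onset reactions only. If f is the share of all reactions that start after 30 minutes, and earlier ones are all seen at 0 or 0.5 h, the overall loss is f × (1 − d). For m = 4 h that is 0.98 f. The documents give no value for f. If f = 0, nothing is lost.

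**Step 5: the other route into the tables.** Section 7.1.3.1 excludes these reactions from adverse event recording, while Section 6 has adverse events assessed throughout. Read together, the two leave the destination of a reaction noticed between scores unstated.

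**The case against.** The strongest reply is that the schedule suits what is known. Section 1.3 links the reactions to injected volume, and a volume effect would plausibly show at or soon after injection, where two of the three scores sit. Nothing in the protocol says to expect onset after 30 minutes. This stands. It limits the likely size of the loss but leaves the interval ungraded.

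It can also be argued that the exclusion in Section 7.1.3.1 covers only reactions found at the scheduled scores. A reaction reported at, say, 6 h would then be an ordinary adverse event under Sections 8.1.1 and 8.2.1. That reading is possible, as is the reading that all five listed reactions stay out of the log. The text does not settle it, which is itself a reason to add a recording rule. Likewise, no text forbids the 24 h grade from looking back, but none asks for it.

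A reader might infer three stronger points that the documents do not support:

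- **Upward bias from the depot.** The triptorelin depot is also given in the abdomen (Protocol 5.1), 10±1 days before dosing. No passage places the two injections at the same spot or suggests that a depot reaction lasts that long.
- **A missed dose trend.** Volumes do rise with dose (12, 18 and 24 µg at 33.3 µg/mL give 0.36, 0.54 and 0.72 mL). But no dose comparison of these reactions is planned, and nothing shows that the gap acts differently by dose.
- **Extra gradings at the PK draws at no cost.** The women are resident and sampled at 4, 8, 12, 16 and 20 h, but Section 7.1.3.1 requires the investigator to grade, and no passage places the investigator at those draws.

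**Conclusion.** The gap is real and follows directly from the schedule. For 23.5 of the 24 hours after injection there is no score, no look-back item and no clear adverse event route for the five listed reactions. A reaction confined to that interval can be absent from every summary table.

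The size of the loss is unknown. It depends on the share of reactions starting after 30 minutes and on how long they last, and the documents give neither. The description of short duration comes from one earlier trial and states no hours. If most reactions start at injection, the loss may be small. The detection rates of 0% to 24% in the working apply only to reactions assumed to start after 30 minutes and must not be read as the endpoint's overall sensitivity.

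This is an inexpensive improvement to a descriptive endpoint. No stated figure is wrong, and the pharmacokinetic analysis is unaffected.

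**What to change.** 1. In Protocol Section 7.1.3.1 and Table 1 footnote g, keep the three current-state grades. Add at 24 h the worst grade of each of the five reactions since the 30-minute score.
2. In SAP Section 10.5, with matching wording in Protocol Section 9.7.3.5, include that worst grade in the any-time row and label it separately from the 24 h current-state grade.
3. In Section 7.1.3.1, state that a listed reaction noticed between scheduled scores is captured in the worst-grade item or, if not there, in the adverse event log.

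Two additions are optional: a look at the intended site before dosing, and grading at existing contacts during the residential stay if the investigator is present.

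Cost: a few more e-CRF fields at an assessment that already takes place, with no added visit or sample. The look-back grade carries some recall error, and reported rates may be somewhat higher. The three existing grades remain available for comparison with earlier trials.
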